10.9. Appendix 9: Abbreviations

Term	Definition
AC	assessment committee
ACR	American College of Rheumatology
ACR20	20% improvement in American College of Rheumatology criteria
ACR50	50% improvement in American College of Rheumatology criteria
ACR70	70% improvement in American College of Rheumatology criteria
ADA	antidrug antibody
AE	adverse event
AESI	adverse event of special interest
AIDS	acquired immune deficiency syndrome
ALT	alanine aminotransferase
ALP	alkaline phosphatase
anti-HBc	hepatitis B core antibody
AST	aspartate aminotransferase
BCG	Bacillus Calmette-Guerin
bDMARD	biologic disease-modifying antirheumatic drug
blinding/masking	A single-blind study is one in which the investigator and/or his staff are aware of the treatment but the participant is not, or vice versa, or when the sponsor is aware of the treatment but the investigator and/his staff and the participant are not. A double-blind study is one in which neither the participant nor any of the investigator or sponsor staff who are involved in the treatment or clinical evaluation of the subjects are aware of the treatment received.
CBD	cannabidiol
C-CASA	Columbia Classification Algorithm of Suicide Assessment
CDAI	Clinical Disease Activity Index
CDC	United States Centers for Disease Control and Prevention
CIOMS	Council for International Organizations of Medical Sciences
Companion diagnostic	An in vitro diagnostic device (assay or test) that provides information that is essential for the safe and effective use of a corresponding therapeutic product

complaint	A complaint is any written, electronic, or oral communication that alleges deficiencies related to the identity, quality, purity, durability, reliability, safety or effectiveness, or performance of a drug or drug delivery system.
compliance	Adherence to all study-related, GCP, and applicable regulatory requirements.
CONSORT	Consolidated Standards of Reporting Trials
CRF	case report form
CRP	C-reactive protein
csDMARD	conventional synthetic disease-modifying antirheumatic drug
CSR	clinical study report
C-SSRS	Columbia-Suicide Severity Rating Scale
CTA	Clinical Trial Agreement
CXR	chest x-ray
DAS28-CRP	Disease Activity Score - C-reactive protein
DAS28-ESR	Disease Activity Score - erythrocyte sedimentation rate
DAS28-hsCRP	Disease Activity Score - high sensitivity C-reactive protein
Device Deficiencies	Equivalent to product complaint
DMARD	disease-modifying antirheumatic drug
DMC	data monitoring committee
ECG	electrocardiogram
eCOA	electronic Clinical Outcome Assessment
eCRF	electronic case report form
EDC	electronic data capture system
enroll	The act of assigning a participant to a treatment. Participants who are enrolled in the study are those who have been assigned to a treatment.
enter	Participants entered into a study are those who sign the informed consent form directly or through their legally acceptable representatives.
ESR	erythrocyte sedimentation rate
EULAR	European League Against Rheumatism
FDA	Food and Drug Administration

FSH	follicle stimulating hormone
GCP	Good Clinical Practice
Gd-DTPA	gadolinium diethylenetriamine penta-acetic acid
HAQ-DI	Health Assessment Questionnaire-Disability Index
HBsAg	hepatitis B surface antigen
HBV	hepatitis B virus
HCV	hepatitis C virus
HIPAA	Health Insurance Portability and Accountability Act
HIV	human immunodeficiency virus
hsCRP	high sensitivity C-reactive protein
IB	Investigator's Brochure
ICF	informed consent form
ICH	International Council for Harmonisation
IEC	Independent Ethics Committees
Ig	immunoglobulin
IGRA	interferon gamma release assay
IL	interleukin
IMP	Investigational Medicinal Product
Informed consent	A process by which a participant voluntarily confirms his or her willingness to participate in a particular study, after having been informed of all aspects of the study that are relevant to the participant's decision to participate. Informed consent is documented by means of a written, signed and dated informed consent form.
INR	international normalized ratio
interim analysis	An interim analysis is an analysis of clinical study data, separated into treatment groups, that is conducted before the final reporting database is created/locked.
investigational product	A pharmaceutical form of an active ingredient or placebo being tested or used as a reference in a clinical trial, including products already on the market when used or assembled (formulated or packaged) in a way different from the authorized form, or marketed products used for an unauthorized indication, or marketed products used to gain further information about the authorized form.
IRB	Institutional Review Boards

IV	intravenous
IWRS	interactive web-response system
LDA	low disease activity
LTBI	latent tuberculosis infection
MAR	missing at random
MedDRA	Medical Dictionary for Regulatory Activities
Medical monitor	Individual responsible for the medical conduct of the study. Responsibilities of the medical monitor may be performed by a clinical research physician, clinical research scientist, global safety physician, or other medical officer designated by the sponsor.
miITT	modified intent-to-treat
MMRM	mixed-effects model for repeated measures
MRI	magnetic resonance imaging
MTX	methotrexate
NIMP	Noninvestigational Medicinal Product
NONMEM	nonlinear mixed effects modeling
NRI	nonresponder imputation
NSAID	nonsteroidal anti-inflammatory drug
OMERACT	Outcome Measures in Rheumatoid Arthritis Clinical Trials
PaGADA_VAS	Patient's Global Assessment of Disease Activity
participant	Equivalent to Clinical Data Interchange Standards Consortium (CDISC) term “subject”: an individual who participates in a clinical trial, either as recipient of an investigational medicinal product or as a control.
PCR	polymerase chain reaction
PD-1	programmed cell death protein 1
PD-L1	programmed cell death ligand 1
PhGADA_VAS	Physician's Global Assessment of Disease Activity
PK/PD	pharmacokinetics/pharmacodynamics
PPD	purified protein derivative
PR	pulse rate

PRO	patient-reported outcomes
Q4W	once every 4 weeks
RA	rheumatoid arthritis
RAMRIS	Rheumatoid Arthritis Magnetic Resonance Imaging Scoring system
RO	receptor occupancy
SAE	serious adverse event
SAP	statistical analysis plan
SC	subcutaneous
screen	The act of determining if an individual meets minimum requirements to become part of a pool of potential candidates for participation in a clinical study.
SDAI	Simplified Disease Activity Index
SERM	selective estrogen receptor modulators
SF-36	Medical Outcomes Study 36-Item Short Form Health Survey
SJC	Swollen Joint Counts
SoA	Schedule of Activities
sPD-1	soluble programmed cell death protein 1
TB	tuberculosis
TBL	total bilirubin level
TE-ADA	treatment-emergent antidrug antibody
TE-ADA+	treatment-emergent antidrug antibody positive
TEAE	treatment-emergent adverse event: An untoward medical occurrence that emerges during a defined treatment period, having been absent pretreatment, or worsens relative to the pretreatment state, and does not necessarily have to have a causal relationship with this treatment.
TJC	Tender Joint Counts
TNF-α	tumor necrosis factor- α
tsDMARD	targeted synthetic disease-modifying antirheumatic drug
TST	tuberculin skin test
ULN	upper limit of normal

VAS visual analog scale

WHO World Health Organization

WOCBP woman of childbearing potential

4.7.1. Other variables and/or parameters.....	32
4.7.2. Subgroup analyses	33
4.8. Interim Analyses.....	33
4.8.1. Data Monitoring Committee (DMC) or Other Review Board.....	34
4.9. Changes to Protocol-Planned Analyses	34
5. Sample Size Determination	35
6. Supporting Documentation	36
6.1. Appendix 1: Demographic and Baseline Characteristics	36
6.2. Appendix 2: Treatment Compliance	36
6.3. Appendix 3: Clinical Trial Registry Analyses	36

Version history

This Statistical Analysis Plan (SAP) for study J1A-MC-KDAD is based on the protocol dated 05AUG2020.

Table 1 SAP Version History Summary

SAP Version	Approval Date	Change	Rationale
1	22DEC2020	Not Applicable	Original version

1. Introduction

This study aims to evaluate the efficacy of LY3462817 in adult participants with moderately to severely active RA who have had an inadequate response to csDMARDs, or to bDMARDs/tsDMARDs. This SAP will summarize the details of statistical analyses in this study.

There are no changes to the analyses described in the protocol.

1.1. Objectives, Endpoints, and Estimands

Objectives	Endpoints
Primary	

 To evaluate the efficacy of LY3462817 in adult participants with moderately to severely active RA. 	
 Change from Baseline of DAS28-CRP at Week 12.
Secondary	

 To describe the safety and tolerability of LY3462817 compared to placebo To evaluate the effect of LY3462817 on measures of disease activity To describe the effect of LY3462817 on PROs To characterize the pharmacokinetics of LY3462817 	
 Safety assessments such as AEs, SAEs Proportion of participants achieving ACR20, ACR50, and ACR70 Change from baseline for physician-assessed individual components: 
 68 tender joint count 66 swollen joint count physician's global assessment of disease activity (VAS) Change from baseline for mean SDAI Change from baseline for mean CDAI Change from baseline for Individual components of the ACR core set: 
 patient's global assessment of disease activity (VAS), patient's global assessment of arthritis pain (VAS), and patient's assessment of physical function (HAQDI) Change from baseline for SF-36 Observed drug concentration
Tertiary/Exploratory	

 To explore the effect of LY3462817 on other measures of disease activity To explore the durability of effect of LY3462817 	
 Proportion of participants achieving LDA or remission using the following measures: DAS28-CRP, DAS28-ESR, SDAI, and CDAI at all time points collected Change from baseline in the RAMRIS synovitis score by MRI imaging

	
 • Proportion of participants achieving LDA (with the following measures: DAS28-CRP, DAS28-ESR, SDAI, and CDAI) at Week 12 and maintaining LDA through Week 24 • Proportion of participants that achieve remission (with the following measures: DAS28-CRP, DAS28-ESR, SDAI, and CDAI) at Week 12 and maintaining remission through Week 24
--	---

Primary estimand

The primary clinical question of interest is: What is the intervention difference in change from baseline of DAS28-CRP after 12 weeks of intervention in participants with Moderately to Severely Active Rheumatoid Arthritis before intervention discontinuation for any reason and before initiation of rescue intervention or change in background intervention? The primary comparison will be assessed using a hypothetical efficacy estimand strategy to address the intercurrent event of early discontinuation where the mean change from baseline will be evaluated using only data up until discontinuation as if all subjects remained on randomized treatment.

The estimand is described by the following attributes:

Population: participants with Moderately to Severely Active Rheumatoid Arthritis. Further details can be found in Section 5.

Endpoint: change from baseline to week 12 in DAS28-CRP

Treatment condition: the randomized treatment without rescue medication or change in background medication (treatment policy strategy). Further details on study interventions and concomitant, including rescue, interventions can be found in Section 6.

The 2 intercurrent events “intervention discontinuation for any reason” and “initiation of rescue intervention or change in background intervention” are both addressed by the treatment condition of interest attribute. There are no remaining intercurrent events.

Population-level summary: difference in mean changes between intervention conditions

Rationale for estimand: The data collected after the treatment discontinuation or post-rescue medication will not represent the true efficacy effects.

Secondary estimands

1) ACR 20/50/70

The clinical question of interest is for the secondary objective regarding Moderately to Severely Active Rheumatoid Arthritis: What is the intervention difference in the percentage of participants achieving ACR20/50/70 after 12 weeks of intervention in participants with Moderately to Severely Active Rheumatoid Arthritis before intervention discontinuation for any reason and before initiation of any interventions affecting ACR20/50/70?

The estimand is described by the following attributes:

Population: participants with Moderately to Severely Active Rheumatoid Arthritis. Further details can be found in Section 5.

Endpoint: achievement of ACR 20/50/70 at week 12

Treatment condition: the randomized intervention without any other interventions (treatment policy strategy). Further details on study interventions and concomitant, including rescue, interventions can be found in Section 6.

The 2 intercurrent events intervention discontinuation for any reason and any interventions affecting ACR 20/50/70 are both addressed by the treatment condition of interest attribute. There are no remaining intercurrent events.

Population-level summary: difference in percentage of participants achieving ACR 20/50/70 at week 12 between intervention conditions

Rationale for estimand: The data collected after the treatment discontinuation or post-rescue medication will not represent the true efficacy effects.

2) Change from baseline in TJC, SJC, PhGADA_VAS, PaGADA_VAS, patient's global assessment of arthritis pain (VAS), HAQ-DI, SF-36, and mean scores of SDAI and CDAI

The clinical question of interest is for the secondary objective regarding Moderately to Severely Active Rheumatoid Arthritis: What is the intervention difference in change from baseline of TJC, SJC, PhGADA_VAS, PaGADA_VAS, patient's global assessment of arthritis pain (VAS), HAQ-DI, SF-36, and mean scores of SDAI and CDAI after 12 weeks of intervention in participants with Moderately to Severely Active Rheumatoid Arthritis before intervention discontinuation for any reason and before initiation of rescue intervention or change in background intervention?

The estimand is described by the following attributes:

Population: participants with Moderately to Severely Active Rheumatoid Arthritis. Further details can be found in Section 5.

Endpoint: change from baseline to week 12 in TJC, SJC, PhGADA_VAS, PaGADA_VAS, patient's global assessment of arthritis pain (VAS), HAQ-DI, SF-36, and mean scores of SDAI and CDAI

Treatment condition: the randomized treatment without rescue medication or change in background medication (treatment policy strategy). Further details on study interventions and concomitant, including rescue, interventions can be found in Section 6.

The 2 intercurrent events “intervention discontinuation for any reason” and “initiation of rescue intervention or change in background intervention” are both addressed by the treatment condition of interest attribute. There are no remaining intercurrent events.

Population-level summary: difference in mean changes between intervention conditions

Rationale for estimand: The data collected after the treatment discontinuation or post-rescue medication will not represent the true efficacy effects.

1.2. Study Design

This is a Phase 2, proof-of-concept, placebo-controlled, double-blind, randomized study in adult participants with moderately to severely active RA who have had an inadequate response to csDMARDs, or to bDMARDs/tsDMARDs. Participants will be administered LY3462817 or placebo IV Q4W.

Screening Period (Visit 1, Days -42 to -1)

Participants will sign the informed consent document(s) at Visit 1, prior to completion of any procedures. Participants will be evaluated for study eligibility ≤ 42 days prior to the baseline visit (Visit 2).

Period 1: Double-blind Treatment (Visits 2 to 6; 12 weeks)

At the baseline visit (Visit 2), participants who fulfill the eligibility criteria will be randomized to receive LY3462817 700 mg, LY3462817 300 mg, or placebo in an allocation ratio of 2:1:1. The double-blind treatment period will establish the clinical efficacy and safety of LY3462817. The study will be evaluated for the primary objective at the end of the double-blind treatment period.

Period 2 (Visits 6 to 10; 12 weeks)

In Period 2, all subjects will receive LY3462817 to assess safety and tolerability data and explore clinical activity with additional dosing. At Week 14, participants will be evaluated for clinical benefit.

Posttreatment Safety Follow-up Period (Visits V801 and 802; 12 weeks)

Following Period 2, participants will be followed posttreatment for 12 weeks to assess safety, study drug exposure, and clinical disease activity measures.

2. Statistical Hypotheses

For the primary estimand with primary endpoint, change from baseline to week 12 in DAS28-CRP, the following 2 (confirmatory) 1-sided hypotheses are planned to be tested for LY3462817 700 mg versus placebo. Let the mean treatment difference be defined as $\mu = (\text{LY3462817 700 mg} - \text{placebo})$.

$H_0: \mu \geq 0.0$ against $H_a: \mu < 0.0$

Operationally the hypotheses will be evaluated by 2-sided tests.

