The PK of LY3462817 has been evaluated following single doses (Study KDAB) and a small subset of the 75 mg multiple dose (Study KDAC) cohort. Nonlinear disposition that is characteristic of many monoclonal antibodies was observed at lower doses and the PK was approximately dose-proportional at doses equal to and greater than 30 mg. Based on noncompartmental analysis, in the dose linear range (≥ 30 mg), LY3462817 has estimated clearance of 10.9 mL/hr, volume of distribution of 3.9 L, and a terminal half-life of approximately 10 days. A comparison of exposure from the single dose 120 mg IV and SC cohorts indicates a bioavailability of approximately 60%. Across the IV cohorts, the median time to reach C_{max} ranges between 2 to 8 hours while for 120 mg SC, the median is approximately 9.5 days. Given the limited PK data in the multiple dose cohort (75 mg IV once every 4 weeks [Q4W]), results were not statistically analyzed. Additionally, in Study KDAB, receptor occupancy (RO) and sPD-1 concentrations in healthy volunteers following single IV doses of LY3462817 were collected and analyzed. Together, both are interpreted as measures of target engagement. Across all dose levels tested, RO and sPD-1 increased in both extent and duration with increasing dose level.

In Study KDAC, the 75-mg cohort (N=8) and 300-mg cohort (N=10) were fully enrolled. By the data cutoff date, some subjects had received a minimum of 2 doses, while some subjects had received a maximum of 4 doses (every-4-week dosing schedule).

A decision was made to dose escalate to 700 mg on 08 September 2020. Given the overall safety profile of LY3462817 to date, the sponsor believes the decision to dose escalate to 700 mg in Study KDAC provides sufficient safety data to initiate this study, KDAD.

A detailed description of the chemistry, pharmacology, toxicology, efficacy, and safety of LY3462817 is provided in the Investigator's Brochure (IB).

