4.1. Overall Design

This is a Phase 2, proof-of-concept, placebo-controlled, double-blind, randomized study in adult participants with moderately to severely active RA who have had an inadequate response to csDMARDs, or to bDMARDs/tsDMARDs. Participants will be administered LY3462817 or placebo IV Q4W.

Screening Period (Visit 1, Days -42 to -1)

Participants will sign the informed consent document(s) at Visit 1, prior to completion of any procedures. Participants will be evaluated for study eligibility \leq 42 days prior to the baseline visit (Visit 2).

Period 1: Double-blind Treatment (Visits 2 to 6; 12 weeks)

At the baseline visit (Visit 2), participants who fulfill the eligibility criteria will be randomized to receive LY3462817 700 mg, LY3462817 300 mg, or placebo in an allocation ratio of 2:1:1.

The double-blind treatment period will establish the clinical efficacy and safety of LY3462817. The study will be evaluated for the primary objective at the end of the double-blind treatment period.

Period 2 (Visits 6 to 10; 12 weeks)

Data from a Study KDAC interim analysis that includes Week 12 data from participants in the KDAC 700-mg cohort, must be reviewed prior to a participant proceeding to Period 2 in Study KDAD.

At Week 14, participants will be evaluated for clinical benefit.

Participants assigned to LY3462817 at baseline, and achieving low disease activity (CDAI \leq 10) at Week 14 will continue to receive LY3462817 at the randomized dose through Week 24 to assess safety and tolerability and evaluate efficacy.

All other participants at Week 14, regardless of baseline treatment assignment, will stop study drug infusions and should receive standard of care treatment at the investigator's discretion.

Posttreatment Safety Follow-up Period (Visits V801 and 802; 12 weeks)

Following Period 2, participants will be followed posttreatment for 12 weeks to assess safety, study drug exposure, and clinical disease activity measures. Participants who discontinue the study intervention per Section 7 will have their last visit at 12 weeks from the last administration of the study intervention.

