6.5.2. Prohibited Concomitant Therapy

Live vaccinations are not allowed up to 3 months prior to screening or at any time during the study. Live herpes zoster vaccination is not permitted within 30 days of planned randomization or at any time during the study.

Nonlive seasonal vaccinations and/or emergency vaccination, such as rabies or tetanus vaccinations, are allowed.

6.5.3. Standard of Care Therapy after Week 14

All placebo patients should begin SOC therapy at Week 14 at the investigator's discretion.

Participants randomized to LY3462817 at baseline and not achieving low disease activity (CDAI ≤ 10) at Week 14 will no longer receive study drug infusions and should receive SOC therapy at the investigator's discretion.

Participants who achieve low disease activity at Week 14, and maintain treatment with LY3462817 during Period 2, can be switched to SOC prior to Week 24 if the participant stops receiving clinical benefit. Name(s) and dosage regimen(s) must be recorded for the SOC therapy. Standard of care medications will not be supplied by the sponsor.

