4.5.6 Disease Activity and PROs

Observed values at baseline and changes from baseline to Week 12 endpoint of disease activity score, PRO score, SF-36 domain score, the physical component score, the mental component

scores will be summarized by treatment arm and provided as listing. An MMRM model, as described in Section 4.3.2, will be used to test the treatment difference of each LY dose versus placebo in change from baseline to Week 12 endpoint.

The frequency and percentage of patients achieving desired response will be summarized by treatment arm at each post-baseline visit. A logistic regression model will be used to test the treatment difference of each LY dose versus placebo at each post-baseline visit with treatment group, baseline value, and previous RA therapy population as model covariates. NRI as described in Section 4.1 will be used to impute missing data for CDAI remission and low disease activity in patients who were Week 12 non-responders or who discontinued prior to Week 12.

For participants who discontinue study intervention and/or receive rescue therapy, post-discontinuation or post-rescue observations will not be included.

4.5.7 Analyses in Period 2

Observed values at baseline and changes from Week 12 to Week 24 endpoint of DAS28-CRP, DAS28-ESR, HAQ-DI, SDAI, CDAI, tender joint count, swollen joint count, Patient's Global Assessment of Arthritis Pain (VAS), Patient's Global Assessment of Disease Activity (PaGADA_VAS), Physician's Global Assessment of Disease Activity (PhGADA_VAS) will be summarized by treatment arm. An MMRM model, as described in Section 4.3.2, will be used to test the treatment difference of each LY dose versus placebo in change from Week 12 to Week 24 endpoint.

The frequency and percentage of patients achieving desired responses on ACR20/50/70 at Week 14 and maintain till Week 24 will be summarized by treatment arm at each period 2 visit. A logistic regression model will be used to test the treatment difference of each LY dose versus placebo at each period 2 visit with treatment group, baseline value at double-blind treatment period, and previous RA therapy population as model covariates. NRI as described in Section 4.1 will be used to impute missing data in patients who were Week 24 non-responders or who discontinued prior to Week 23.

For participants who discontinue study intervention and/or receive rescue therapy, post-discontinuation or post-rescue observations will not be included.

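### SAP section 1.2 puts every participant on LY3462817 in Period 2, against the supplied protocol; the Week 16 to 24 LY-versus-placebo tests have no placebo control, and the SAP's safety grouping and windows conflict

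*SAP*

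**What the plan says.** **Who is treated in Period 2.** SAP 1.2: "In Period 2, all subjects will receive LY3462817 to assess safety and tolerability data and explore clinical activity with additional dosing". Protocol 4.1 keeps on study drug only those randomized to LY3462817 who reach CDAI ≤10 at Week 14, and adds: "All other participants at Week 14, regardless of baseline treatment assignment, will stop study drug infusions and should receive standard of care treatment". Protocol 6.5.3 is explicit about the control arm: "All placebo patients should begin SOC therapy at Week 14". The Schedule of Activities gives infusions at Weeks 16 to 24 only to participants with low disease activity at Week 14. The SAP also disagrees with itself: its exposure section (4.6.1) limits Period 2 exposure to those still on one of the two LY doses.

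**Period 2 efficacy.** SAP 4.5.7 applies the primary mixed model (MMRM) to test "each LY dose versus placebo in change from Week 12 to Week 24 endpoint", and excludes observations after discontinuation or rescue. SAP 4.5.1 to 4.5.4 repeat the remission and low-disease-activity comparisons at all Period 2 visits with nonresponder imputation (NRI). Under SAP 4.1, NRI makes anyone who permanently discontinues before the end of the treatment period a nonresponder.

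**Safety.** SAP 3 groups by intervention received, and protocol 9.3 does the same within each study period. SAP 4.6 groups by assigned treatment. SAP 4.1 defines the Treatment Period as Periods 1 and 2 together but ends its post-baseline window at Week 12; SAP 4.6.2 judges treatment emergence up to Week 24.

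**The concern.** Correcting the sentence in SAP 1.2 would not by itself change any table. The rules further down the SAP assume a placebo comparator through Week 24, and under the protocol nobody receives a placebo infusion after Week 12. The SAP does not define rescue, and does not say whether the planned Week 14 stop, or the standard of care that follows, counts as discontinuation or rescue. Two programmers could produce different Period 2 results from the same text, one of them with no estimate at all.

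For safety, the SAP does not settle whether an event at Week 20 in someone who left infusions at Week 14 belongs to the assigned arm. At stake are the exploratory durability results through Week 24 and the Period 2 safety tables; safety is a secondary objective.

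**Working it through.** **Inputs.** Planned arms of 40 (700 mg), 20 (300 mg) and 20 (placebo), from protocol 9.2. Infusions for everyone at baseline and Weeks 4, 8 and 12; visits at Weeks 14, 16, 20 and 24 (Schedule of Activities). Half-life from protocol 2.2: "a terminal half-life of approximately 10 days". All counts assume planned sizes and full follow-up.

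**1. The plan's own figure.** The only calculable design figure is the power at Week 12. Difference 1.80 − 0.75 = 1.05; standard error 1.25 × √(1/40 + 1/20) = 0.342; ratio 3.07. Two-sided 0.05 power is 85.5% (noncentral t, 58 df) or 86.6% (normal approximation). The stated figure of more than 80% is reproduced, and nothing below touches it.

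**2. Mixed model, if the stop or standard of care counts as discontinuation or rescue.** For an endpoint measured at Weeks 16, 20 and 24, such as DAS28-CRP, placebo contributes 0 of 20 × 3 = 60 scheduled observations. With three arms and four visits (Weeks 14, 16, 20, 24), the treatment-by-visit part has 12 parameters. With every cell filled the rank is 12 and the Week 24 contrast of 700 mg against placebo is estimable. With three placebo cells empty the rank is 9, and adding the contrast raises it to 10, so the contrast is not estimable.

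**3. Responder tests, if the stop counts as discontinuation.** NRI sets placebo to 0/20 at Weeks 16 to 24. Once any LY participant responds, the logistic odds ratio has no finite maximum-likelihood estimate. As a gauge, two-sided Fisher tests against 0/20:

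| Arm | Responders | p |
|---|---|---|
| 700 mg | 7/40 | 0.084 |
| 700 mg | 8/40 | 0.043 |
| 300 mg | 4/20 | 0.106 |
| 300 mg | 5/20 | 0.047 |

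These p-values hold whatever the former placebo participants' actual disease activity.

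**4. If the stop counts as neither.** The data can be fitted, but the group labelled placebo is off infusions and on standard of care. Each LY arm mixes continuers, selected on Week 14 response, with participants who also moved to standard of care. That is not a test of LY against placebo.

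**5. Safety person-time, read as SAP 4.6 and 4.6.2 state.** Placebo arm: 20 × 24 = 480 person-weeks, of which 20 × 10 = 200 (41.7%) follow the Week 14 switch. Counted from the last placebo infusion at Week 12, it is 20 × 12 = 240 (50%). LY arms: 60 × 24 = 1,440 person-weeks, of which 600 × (1 − p) follow a stop, where p is the share with CDAI ≤10 at Week 14. The documents do not give p, so the range is 0% to 41.7%. Under SAP 4.1's Week 12 post-baseline window the share is 0%.

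**6. Drug remaining after a stop.** Assuming single-exponential decline, 0.5^(14/10) = 0.379 of the Week 12 level remains at Week 14, and five half-lives end at (84 + 50)/7 = Week 19.1. Early events after stopping may still be drug-related, so time since last infusion should stay visible.

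**The case against.** **Version lag.** The SAP "is based on the protocol dated 05AUG2020", while the supplied protocol reports a later event: "A decision was made to dose escalate to 700 mg on 08 September 2020". This probably explains the mismatch. A reader might infer that the SAP misreported its own source; that is not supported, because the August text is not available and the supplied protocol's date is not visible. Lag does not make the later rules workable.

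**The protocol rule is not the sole cause.** Under SAP 1.2's own design, placebo participants would be on LY3462817 in Period 2, so there would be no placebo control either. The conflict between assigned and received treatment also exists under both designs. Both points stand, and both mean that the tests and the grouping need changing in any case.

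**The planned stop is probably not a discontinuation.** Protocol 7.1.2 does not list it and treats permanent discontinuation as rare. Section 6.5.3 presents it as a scheduled transition, visits continue to Week 24, and the Period 2 concomitant-therapy rules cover only those still on LY. This is the better-supported reading. A reader might take 0/20 as the plan's certain outcome, and from it infer a high false-positive rate: 24% at a 15% low-disease-activity rate and 56% at 20%, for 700 mg with no drug effect and no loss of response. The documents support neither inference. They give no such rates, and 0/20 follows only on the less supported reading. What remains is that the SAP leaves the reading open, its undefined rescue term could still trigger the exclusion, and the better-supported reading still gives a standard-of-care comparator.

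**Larger safety shares.** A reader might stretch the window to 24 weeks after the last infusion, which SAP 4.1 allows for Period 2. That should not be combined with the discontinuation reading: protocol 4.1 ends follow-up 12 weeks after the last dose for participants who discontinue under Section 7.

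**Weeks 12 to 14 are still randomized.** Everyone receives the Week 12 infusion as assigned, and nothing changes until Week 14. Cutting comparisons at Week 12 would discard up to 80 × 2 = 160 valid person-weeks. This stands and sets the cut-off in the fix.

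**Conclusion.** The SAP is wrong as written on Period 2 treatment, and its analyses at Weeks 16 to 24 cannot be run as LY against placebo on any reading. The result is no estimable contrast, a placebo response fixed at 0/20, or a standard-of-care group under a placebo label. Which of these applies depends on a definition that the SAP omits; that a placebo control is missing does not.

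The safety conflict needs no such assumption. Its size, 41.7% of placebo-arm person-weeks after the Week 14 switch, rests on planned arm sizes, full follow-up, and SAP 4.6 and 4.6.2 taken literally.

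A reader might infer that the main result is compromised or that placebo participants would be given LY3462817. Neither follows: the Week 12 primary analysis and its power are unaffected, and dosing is governed by the protocol. The Period 2 efficacy analyses are exploratory. This should be corrected before unblinding, but it is not a threat to the trial's primary conclusion.

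**What to change.** (a) Replace the Period 2 paragraph of SAP 1.2 with the rule in protocol 4.1, and update the protocol version cited.

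(b) In SAP 4.6, group safety by the intervention received within each study period, as in protocol 9.3. Use one Treatment Period end in 4.1 and 4.6.2.

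(c) Keep randomized LY-versus-placebo comparisons, for efficacy and safety, through the Week 14 assessment and before the switch. Count Weeks 12 to 14 to the randomized intervention given at Week 12.

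(d) After Week 14, make 4.5.7, the Period 2 parts of 4.5.1 to 4.5.4 and the safety summaries descriptive in three groups: LY continued, LY stopped and former placebo. Show randomized dose and time since last infusion. State that the planned Week 14 switch triggers neither the post-discontinuation and post-rescue exclusion nor the NRI discontinuation criterion.

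The cost is wording in those SAP sections and one derived grouping variable. No new data are needed: arm, Week 14 CDAI and infusion dates are already collected, and protocol 6.5.3 requires that "Name(s) and dosage regimen(s) must be recorded for the SOC therapy".
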